10.9 Exploratory analysis

Exploratory analysis may be performed for PFS and OS adjusted for baseline prognostic factors such as total prior regimens, GPNMB expression levels, stromal GPNMB expression levels, and other factors using multivariate Cox proportional hazards models.

In addition, exploratory analysis of rash in cycle 1 will be performed to assess its correlation with clinical outcomes.

11 STUDY TREATMENT

CDX-011 will be administered as an intravenous infusion over 90 (\pm 10) minutes on Day 1 of each 21 day cycle. Subjects will continue to be dosed once every three weeks until disease progression or unmanageable treatment-related toxicities.

The duration of exposure to study treatment, total number of cycles initiated, cumulative dose administered, and relative dose intensity will be summarized. The calculation for the above statistics is specified below:

- Duration of Exposure (days) = Date of first dose of last cycle – Date of first dose + 21 days
- For CDX-011, the actual dose at each cycle (mg/kg) = Total Vol infused (mL) / [Vol of Infusion bag (mL)] * Volume of CDX-011 added to bag (mL) * 5 (mg/mL) / Weight at the cycle (kg).
- For capecitabine, the actual dose at each cycle (mg/m²) = Total doses at each cycle (mg) / BSA (m²).
- Cumulative dose is the sum of all actual doses for all cycles.
- Actual dose intensity (ADI) = Cumulative Dose / Duration of Treatment (weeks).
- Relative Dose Intensity = Actual Dose Intensity / Planned Dose Intensity (PDI).

Dose modifications and reasons will be summarized by treatment. For CDX-011, dose modifications include dose delayed since last dose, dose reduced since the last dose, infusion interrupted, infusion slowed, infusion prematurely discontinued, and other. For capecitabine, dose modifications include dose delayed/interrupted since the last dose, dose level reduced since the last dose, prematurely discontinued, and other.

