
Study Treatment Dosing and Administration
	
CDX-011 will be administered on Day 1 of repeated 21 day cycles. The starting CDX-011 dose is 1.88 mg/kg, given as a 90-minute intravenous infusion using a 0.22 µm in-line filter. Treatment will continue until progression or intolerance.
 
Capecitabine will be orally administered on Days 1-14 of repeated 21 day cycles. The recommended capecitabine starting dose is 1250 mg/m² twice daily (equivalent to 2500 mg/m² total daily dose) per the package insert, and subsequent treatment will be dictated by tolerance and institutional practice.

Eligibility Criteria
	
Inclusion Criteria
 
Patients may be included in the study only if they meet all of the following inclusion criteria at the time of randomization:
 
 1. Female or male subjects with metastatic, histologically or cytologically confirmed carcinoma of the breast. 2. Documented progression of disease, based on radiographic, clinical or pathologic assessment showing increased tumor burden or new site(s) of disease during or subsequent to the last anticancer regimen received. 3. Overexpression of GPNMB ($\geq 25\%$ of malignant epithelial cells expressing GPNMB, as determined by a central laboratory using IHC methods) in at least one tumor sample obtained in the advanced setting. 4. Triple-negative status determined in a tumor sample obtained in the advanced setting, according to the following criteria: 
 a. Minimal or no expression of estrogen and progesterone receptors ($<10\%$ of cells positive by immunohistochemistry (IHC)). Patients with low hormone receptor expression (ER and/or PR 1-9%) must be deemed appropriate candidates for cytotoxic chemotherapy by the investigator. b. Minimal or no expression of HER2 (IHC staining of 0 or 1+; ISH single-probe average HER2 copy number < 4.0 signals/cell; or ISH dual-probe HER2/CEP17^a ratio < 2.0 with an average HER2 copy number < 4.0 signals/cell). (Wolff, Hammond et al. 2014):

^aAlso referred to as CEN17.

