8.2.4. Dose Modifications

Capecitabine dosage may need to be individualized to optimize patient management. Patients should be carefully monitored for toxicity and doses of capecitabine should be promptly modified as necessary to accommodate individual patient tolerance to treatment. Toxicity due to capecitabine administration may be managed by symptomatic treatment, dose interruptions and adjustment of capecitabine dose. Once the dose has been reduced, it should not be increased at a later time. Doses of capecitabine omitted for toxicity are not replaced or restored; instead the patient should resume the planned treatment cycles.

Management of capecitabine toxicity, dosing, dose reductions and supportive care should be consistent with the package insert recommendations, but should be dictated by institutional and investigator standard practice and the need for individual patient management. [Table 6](#) outlines

the recommended capecitabine dose modification scheme for the management of adverse reactions.

Table 6. Recommended Dose Modifications of Capecitabine

Toxicity NCIC Grades*	During a Course of Therapy	Dose Adjustment for Next Treatment (% of starting dose)
Grade 1		
	Maintain dose level	Maintain dose level
Grade 2		
-1st appearance	Interrupt until resolved to grade 0-1	100%
-2nd appearance		75%
-3rd appearance		50%
-4th appearance	Discontinue treatment permanently	-
Grade 3		
-1st appearance	Interrupt until resolved to grade 0-1	75%
-2nd appearance		50%
-3rd appearance	Discontinue treatment permanently	-
Grade 4		
-1st appearance	Discontinue permanently OR If physician deems it to be in the patient's best interest to continue, interrupt until resolved to grade 0-1	50%

*National Cancer Institute of Canada Common Toxicity Criteria were used except for the hand-and-foot syndrome (see [Section 8.2.5.4](#)).

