12.5.3. Safety Analysis

Safety and tolerability will be assessed by incidence, severity, and changes from baseline of all relevant parameters including adverse events (AEs), ECGs, laboratory values, and vital signs.

AEs will be coded using the latest available version of the Medical Dictionary for Regulatory Activities (MedDRA). The number and percentage of patients experiencing one or more AEs will be summarized by treatment arm, relationship to study drug, and severity. Laboratory parameters will be summarized using descriptive statistics, by post-dosing shifts relative to baseline, and data listings of clinically significant abnormalities. Treatment-emergent AEs are defined as AEs that start on or after the first day study drug is administered. AEs will be summarized by the number and percentage of patients who experienced the event, according to system organ class and preferred term. A patient reporting multiple cases of the same AE will be counted once within each system organ class and similarly counted once within each preferred term. Unless specified otherwise, the denominator for these calculations will be based on the number of patients in each

treatment arm who receive at least one (1) dose of study drug, irrespective of the total number of doses administered. AEs will also be summarized by NCI-CTCAE severity grade and by relationship to study drug. Additional summaries may also be provided for SAEs and events resulting in the permanent discontinuation of therapy. All AEs will be included in individual patient data listings.

Vital sign results (systolic and diastolic blood pressure, pulse, respiration, and temperature) and ECG parameters will be summarized descriptively. Changes will be calculated relative to the assessments at baseline.

The changes in hematology, chemistry, and other laboratory values will be summarized descriptively. The incidence of Grade 3 and 4 hematological toxicities (including neutropenia, thrombocytopenia, and anemia) will be provided. The use of red blood cell and other blood component transfusions and/or growth factor support will be reported. Similar analyses will be done for selected chemistry tests (including liver and renal function tests). Data listings of all laboratory data collected during the study will be presented. Laboratory values outside normal limits will be identified in data listings and will include flags for high and low values.

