12.2 Adverse Events

Summary tables and listings will be provided for all reported treatment emergent adverse events. Treatment emergent adverse events (TEAEs) are defined as adverse events that start on or after the first administration of study treatment and through 28 days after the last dose of study treatment. If it cannot be determined whether an adverse event is treatment-emergent (based on AE start date or, if AE start date is missing or partial AE start date), conservatively, the adverse event will be considered treatment-emergent event.

For partially missing AE start dates (missing day and/or month), the following imputation rules will be applied:

If both day and month of the AE start date are missing, the day and month will be imputed with the day and month of the first study dose date if the year is equal to the year of the first dose. Otherwise, the month and day is imputed as the first day of the year (01 Jan).

If only day is missing, and if the year and month are equal to the first dose date, the AE start date will be imputed as the first dose date. Otherwise, the day will be imputed as "01". As a general consideration, imputed AE start date cannot be after AE end date if available.

The reported adverse event term will be assigned standardized terms using the Medical Dictionary for Regulatory Activities (MedDRA). The version of MedDRA that is actually used for this study will be noted in the clinical study report.

Treatment emergent adverse events will be summarized based on the number and percentage of patients experiencing events by MedDRA system organ class and preferred term. The causal relationship between the occurrence of an adverse event and study treatment will be judged by the investigator as “related” or “unrelated”. A worst-case scenario approach will be taken to handle missing relatedness data, i.e. the summary table of treatment-related AEs will include events with the relationship to study treatment reported as “Related” or “Missing”. In the event a patient experiences multiple episodes of the same adverse event, then the event with the highest severity grade and/or strongest causal relationship to study treatment will be used for purposes of incidence tabulations.

Tabular summaries of the following treatment emergent adverse events will be provided:

- Overview of TEAEs
- TEAEs by SOC and PT
- Treatment-related TEAEs by SOC and PT
- TEAE by PT by decreasing frequency
- TEAEs by SOC and PT and worst toxicity grade

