- Treatment-related TEAEs by SOC and PT and worst toxicity grade
- TEAEs with action of study treatment delayed/interrupted
- TEAEs with action of treatment reduced
- TEAEs with action of study treatment discontinued
- Serious TEAEs by SOC and PT
- Treatment-related serious TEAE by SOC and PT
- TEAEs with fatal outcome by SOC and PT
- Treatment-related TEAEs with fatal outcome by SOC and PT

In addition to the tabular summaries, adverse events will be reported in individual patient listings.

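### One combined delayed/interrupted adverse-event table is not like-for-like between a 14-day oral schedule and a Day 1 infusion; report the components as separate rows

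*SAP*

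**What the plan says.** **Schedules.** The Protocol synopsis states "Capecitabine will be orally administered on Days 1-14 of repeated 21 day cycles" and "CDX-011 will be administered on Day 1 of repeated 21 day cycles". For capecitabine toxicity of Grade 2 or 3, Table 6 in Protocol 8.2.4 recommends "Interrupt until resolved to grade 0-1". At Grade 4 it gives this as an alternative to stopping for good.

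**Adverse-event table.** The list of tables in SAP 12.2 has one entry for this action: "TEAEs with action of study treatment delayed/interrupted". Reductions and discontinuations have their own entries. Protocol 12.5.3 makes the presentation by arm: "The number and percentage of patients experiencing one or more AEs will be summarized by treatment arm, relationship to study drug, and severity". The counting unit is the patient: SAP 12.2 has TEAEs "summarized based on the number and percentage of patients experiencing events by MedDRA system organ class and preferred term", and Protocol 12.5.3 counts repeat cases of a term once.

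**Dose-modification summary.** SAP 11 is a different output with its own list for each arm. One list reads: "For CDX-011, dose modifications include dose delayed since last dose, dose reduced since the last dose, infusion interrupted, infusion slowed, infusion prematurely discontinued, and other". The other reads: "For capecitabine, dose modifications include dose delayed/interrupted since the last dose, dose level reduced since the last dose, prematurely discontinued, and other". Delay and interruption are therefore separate items on CDX-011 and a single item on capecitabine.

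**Not available for checking.** The CDX-011 dose-modification section (Protocol 8.1.6) is not in the text reviewed, and SAP 16 places the table shells in a separate document. Neither gap is a fault in the plan.

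**The concern.** The category covers different things in the two arms. On capecitabine it takes in any tablets withheld on Days 1-14 as well as a late start to the next cycle. On CDX-011 there is no dose to hold between infusions, so a toxicity that starts after the infusion and resolves before the next Day 1 leaves no trace in the row. What CDX-011 can contribute is a late infusion and perhaps a pause during one.

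Identical toxicities could therefore give different percentages because of the calendar. SAP 11 does not repair this, because it has no capecitabine cycle-delay item to set beside the CDX-011 one. At stake is how a reader interprets one by-arm tolerability table in an open-label pivotal trial, where further characterizing CDX-011 safety is a secondary objective.

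**Working it through.** The documents give no rate or ratio for this table, so there is no figure to reproduce. The size below comes from counting days.

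**Inputs from the documents**
- Cycle of 21 days; capecitabine on Days 1-14, CDX-011 on Day 1 (Protocol synopsis).
- One documented short duration: a median of 5 days for Grade 3-4 diarrhea on capecitabine (Protocol 8.2.5.1).
- Planning median PFS of 4.0 and 6.25 months (SAP 5).

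**Assumptions**
- Onset is equally likely on each of Days 1-21, and the event lasts d days.
- Both drugs are held at the same severity, and every such event leads to a hold.
- CDX-011 infusion pauses are not counted.

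**Step 1, per event.** Capecitabine registers if any toxic day is a dosing day: onset on Days 1-14, or still present on Day 22. CDX-011 registers only if the event is present on Day 22. The probabilities are min(14 + d - 1, 21)/21 and min(d - 1, 21)/21.

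| Duration (days) | Capecitabine | CDX-011 | Ratio |
|---|---|---|---|
| 3 | 16/21 = 76% | 2/21 = 10% | 8.0 |
| 5 | 18/21 = 86% | 4/21 = 19% | 4.5 |
| 7 | 20/21 = 95% | 6/21 = 29% | 3.3 |
| 10 | 21/21 = 100% | 9/21 = 43% | 2.3 |
| 14 | 100% | 13/21 = 62% | 1.6 |
| 21 | 100% | 20/21 = 95% | 1.05 |
| 22 or more | 100% | 100% | 1.0 |

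A continuous-time version gives ratios of 3.8 at 5 days and 3.0 at 7 days. For a 5-day event the whole gap comes from onset on Days 1-14 (100% vs 0%). For onset on Days 15-21 the arms agree (4/7 = 57% each).

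**Step 2, per patient.** This is the unit the table uses. With event probability q per cycle, independent cycles and K cycles, incidence = 1 - (1 - q*p)^K, where p is the Step 1 probability. The planning medians give 4.0 x 30.4375/21 = 5.8 and 6.25 x 30.4375/21 = 9.1 cycles, hence K = 6 and 9. For a 5-day toxicity:

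| q | Capecitabine, K = 6 | CDX-011, K = 6 (ratio) | CDX-011, K = 9 (ratio) |
|---|---|---|---|
| 0.05 | 23.1% | 5.6% (4.1) | 8.3% (2.8) |
| 0.2 | 67.6% | 20.8% (3.3) | 29.5% (2.3) |
| 0.5 | 96.5% | 45.1% (2.1) | 59.4% (1.6) |

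Over the same settings the ratio is 1.0 to 1.5 for a 14-day toxicity. At 21 days it is 1.01 to 1.04 with equal cycles and 0.75 to 0.99 with 6 vs 9 cycles.

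**Step 3, with the rows separated.** For a 5-day toxicity, any delay of the next cycle start occurs in 4/21 = 19% of events in both arms, a ratio of 1.0. The capecitabine within-cycle holds (14/21 = 67%) get their own row.

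**Step 4, the delay threshold matters.** A 5-day event with onset on Days 18-21 ends on Days 22-25, so dosing resumes on Days 23-26, which is 1 to 4 days late. The Table 1 window of 5 days from Cycle 3 onward absorbs all four cases; the 3-day window at Cycle 2 absorbs three. If only delay beyond the window counted, the 4/21 would become 0/21 from Cycle 3 onward and 1/21 at Cycle 2.

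**The case against.** The case on the other side is substantial.

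- **Standing of the row.** Delay or interruption is not among the safety endpoints in SAP 3.4, and no test is planned on it. The tables by preferred term and worst grade, serious events, reductions, discontinuations and relative dose intensity give context. This stands, and it makes the point a modest one.
- **SAP 11 is a different output.** It already separates delay from infusion interruption on CDX-011. This also stands. The main evidence is the single entry in SAP 12.2; SAP 11 shows only that a capecitabine cycle-delay item is missing there too.
- **Size depends on assumptions.** Equal hold thresholds cannot be checked without Protocol 8.1.6. Table 6 is a recommendation, and Protocol 8.2.4 leaves capecitabine management to institutional and investigator practice. The 5-day figure describes one capecitabine toxicity. Infusion pauses, if mapped to this row, would raise the CDX-011 figure. All of this stands.
- **The shells may already split the row.** That is possible; SAP 12.2 should then say so.

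Three stronger readings are tempting. A reader might infer that the table will make CDX-011 look better tolerated whatever the toxicity. The documents do not support that: the effect fades with duration, is absent for late-cycle onset, and can reverse per patient when CDX-011 exposure is longer. A reader might take the per-event gap (67 points at 5 days) as the gap the table will show. It is not, because the table counts patients. And a reader might conclude that capecitabine holds are falsely counted, or that arms should be compared on cycle delay and not on holds. The holds are real treatment actions and belong in the safety report.

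**Conclusion.** The point holds as one of comparability. SAP 12.2 puts into a single by-arm category an action that can occur on 14 days per cycle in one arm and at one infusion in the other, and no supplied text separates the components. For short toxicities the calendar alone then favours CDX-011: 86% vs 19% per event at 5 days, and roughly 1.6 to 4.1 times per patient, moving to about 1 at three weeks or more. These sizes rest on uniform onset, equal hold thresholds, assumed event rates of 0.05 to 0.5 per cycle, and 6 vs 6 or 6 vs 9 cycles. The direction for short toxicities follows from the schedules if hold thresholds are similar. The table is descriptive; the PFS analysis, its alpha and the sample size are untouched.

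**What to change.** In SAP 11 and 12.2, report these rows by arm:

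- (a) Next cycle start delayed, with an adverse event as the recorded reason. Derive it identically in both arms from the cycle-start dates defined in SAP 7.4, with a stated threshold. One choice is any delay beyond the planned Day 1, with delay beyond the Table 1 window shown additionally. The reason is needed because Table 1 footnote 1 allows delays for holidays and weather.
- (b) Capecitabine within-cycle interruption.
- (c) CDX-011 infusion interrupted or slowed.

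Footnote that (b) and (c) reflect different schedules and are not like-for-like. The combined row can stay if wanted. If the shells already make this split, a sentence in SAP 12.2 is enough.

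The cost is SAP wording and one extra descriptive table, built from dose dates and modification reasons the plan already uses. The combined row becomes less simple to read. No dosing rule or data collection changes.

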12 SAFETY ANALYSES

12.1 General Considerations

Safety will be assessed by clinical review of all relevant parameters including adverse events (AEs), serious adverse events (SAEs), laboratory values (hematology, serum chemistry, and urinalysis), vital signs, physical examinations, 12-lead electrocardiograms (ECGs), and ECOG performance status. The safety analyses will be performed using the safety population defined in [Section 6.2](#).

12.2 Adverse Events

Summary tables and listings will be provided for all reported treatment emergent adverse events. Treatment emergent adverse events (TEAEs) are defined as adverse events that start on or after the first administration of study treatment and through 28 days after the last dose of study treatment. If it cannot be determined whether an adverse event is treatment-emergent (based on AE start date or, if AE start date is missing or partial AE start date), conservatively, the adverse event will be considered treatment-emergent event.

For partially missing AE start dates (missing day and/or month), the following imputation rules will be applied:

If both day and month of the AE start date are missing, the day and month will be imputed with the day and month of the first study dose date if the year is equal to the year of the first dose. Otherwise, the month and day is imputed as the first day of the year (01 Jan).

If only day is missing, and if the year and month are equal to the first dose date, the AE start date will be imputed as the first dose date. Otherwise, the day will be imputed as "01". As a general consideration, imputed AE start date cannot be after AE end date if available.

The reported adverse event term will be assigned standardized terms using the Medical Dictionary for Regulatory Activities (MedDRA). The version of MedDRA that is actually used for this study will be noted in the clinical study report.

Treatment emergent adverse events will be summarized based on the number and percentage of patients experiencing events by MedDRA system organ class and preferred term. The causal relationship between the occurrence of an adverse event and study treatment will be judged by the investigator as “related” or “unrelated”. A worst-case scenario approach will be taken to handle missing relatedness data, i.e. the summary table of treatment-related AEs will include events with the relationship to study treatment reported as “Related” or “Missing”. In the event a patient experiences multiple episodes of the same adverse event, then the event with the highest severity grade and/or strongest causal relationship to study treatment will be used for purposes of incidence tabulations.

Tabular summaries of the following treatment emergent adverse events will be provided:

- Overview of TEAEs
- TEAEs by SOC and PT
- Treatment-related TEAEs by SOC and PT
- TEAE by PT by decreasing frequency
- TEAEs by SOC and PT and worst toxicity grade
- Treatment-related TEAEs by SOC and PT and worst toxicity grade
- TEAEs with action of study treatment delayed/interrupted
- TEAEs with action of treatment reduced
- TEAEs with action of study treatment discontinued
- Serious TEAEs by SOC and PT
- Treatment-related serious TEAE by SOC and PT
- TEAEs with fatal outcome by SOC and PT
- Treatment-related TEAEs with fatal outcome by SOC and PT

In addition to the tabular summaries, adverse events will be reported in individual patient listings.

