followed by the same methodology (i.e., CT or MRI scan). However, bone lesions followed as non-target disease may be subsequently followed by bone scans only. Lesions that cannot be imaged but are assessable by clinical exam may be assessed using color photography including a ruler (preferred method) or measured with calipers. Normally, all target and non-target disease sites should be evaluated at each assessment. However, for patients with non-target bone disease, bone scans need only be repeated every twelve weeks. The same method of assessment and the same technique should be used to characterize each identified and reported lesion at baseline and during follow-up. Target lesions selected for tumor measurements should be those where surgical resection or radiation are not indicated or anticipated.

25. Randomization may be performed up to 5 days prior to initiation of study treatment, but should occur only after confirming all eligibility criteria have been met.
26. Unless otherwise specified, all study assessments should be performed prior to administration of study treatment, and may be performed up to 24 hours prior to treatment administration if assessments remain within the specified visit window.
27. All concomitant medication will be documented in the CRF if taken within 28 days prior to Study Day 1, and either (whichever occurs sooner): a) 28 days after last dose of study treatment or b) initiation of alternate anti-cancer therapy. In addition, all anti-cancer medications and concomitant medications required to treat CDX-011-related SAEs taken throughout the duration of study follow-up should also be recorded.
28. For patients who develop grade 3 rash possibly related to CDX-011 and who provide appropriate consent, punch biopsies and photographs of the rash site, as well as uninvolved skin, are strongly encouraged. Samples may be submitted for central analyses including quantification of GPNMB expression; in these cases, collection, processing and shipping instructions will be provided separately.
29. Adverse event monitoring on Cycle 1 Day 7 and Cycle 1 Day 14 can be performed in person or by telephone to determine if the patient is experiencing any adverse events.
30. Events occurring > 28 days after discontinuation of study treatment are only reportable if serious (SAE) and potentially treatment-related.

[REDACTED]

[REDACTED]

[REDACTED]

[REDACTED]

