10.2.2.3. AE/SAE Reporting

The investigator is to report all directly observed adverse events and all adverse events spontaneously reported by the study subject. In addition, each study subject will be questioned about adverse events.

Adverse Events (AEs) and Serious Adverse Events (SAEs) should be recorded on the CRF from the time the subject has taken at least one dose of study treatment (CDX-011 or capecitabine) through (whichever occurs first) either a) 28 calendar days after the last administration of study treatment, or b) initiation of alternate anticancer therapy.

However:

- Any SAE occurring any time after the reporting period must be promptly reported if a causal relationship to study treatment is suspected
- For AEs or SAEs with a causal relationship to the investigational product, follow-up by the investigator is required until the event or its sequelae resolve to \leq Grade 1, or stabilize for at least three months after the last administration of study treatment (whichever is sooner).

All adverse events will be reported on the adverse event page(s) of the CRF, while SAEs will also be reported in an expedited fashion using the Serious Adverse Event Report. The AE CRFs and SAE Reports must be completed in a consistent manner; for example, the same adverse event term, causality, severity, and onset/resolution dates should be used on both forms.

In case of a serious adverse event (regardless of causality), a Serious Adverse Event Report must be completed and submitted to the sponsor (or sponsor's designated representative) within 24 hours of the site's notification of the event, irrespective of the extent of available adverse event information. This timeframe also applies to additional new information (follow-up) on previously forwarded serious adverse event reports. The investigator is obligated to pursue additional information required for thorough evaluation of each SAE as may be requested by Celldex Therapeutics, Inc. (or designee).

Serious adverse event reporting to regulatory authorities and all participating investigators will be conducted by Celldex Therapeutics, Inc. (or designee) in accordance with 21CFR312.32 and international regulations, as appropriate.

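### SAP 12.2 ends the treatment-emergent window 28 days after last dose and tabulates only treatment-emergent events, so a later drug-related SAE that the protocol still requires to be reported enters no AE incidence table

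*SAP*

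**What the plan says.** **Definition.** Protocol 12.5.3 sets a start and no finish: "Treatment-emergent AEs are defined as AEs that start on or after the first day study drug is administered". SAP 12.2 sets both, requiring that the event "start on or after the first administration of study treatment and through 28 days after the last dose of study treatment".

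**Collection.** Protocol 10.2.2.3 ends routine recording at whichever comes first: "28 calendar days after the last administration of study treatment, or b) initiation of alternate anticancer therapy". It then makes an exception: "Any SAE occurring any time after the reporting period must be promptly reported if a causal relationship to study treatment is suspected". Footnote 30 of the assessment schedule, which the SAP repeats in its own Table 1, agrees: "Events occurring > 28 days after discontinuation of study treatment are only reportable if serious (SAE) and potentially treatment-related".

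**Tables.** SAP 12.2 introduces its list with "Tabular summaries of the following treatment emergent adverse events will be provided". The list includes "Treatment-related serious TEAE by SOC and PT" and "Treatment-related TEAEs with fatal outcome by SOC and PT". It contains no summary of events that start after the window.

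**Elsewhere.** The end of SAP 12.2 promises patient listings of adverse events, in a sentence not confined to treatment-emergent ones. SAP 12.4 lists all on-study deaths with cause and days since last dose, and summarizes primary cause of death by arm. SAP Section 14, the place for changes from the protocol, records only a clarification about ORR.

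**The concern.** Beyond 28 days after treatment, the only events the protocol still asks sites to report are those that are both serious and suspected to be drug-related. The SAP's window excludes exactly that class from its incidence tables. The protocol's own definition would treat such events as treatment-emergent, and protocol 12.5.3 plans AE summaries by arm and by relationship to study drug.

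At stake are the related-serious and related-fatal rates by arm. They are among the main safety figures in a pivotal trial report, and they can rest on small counts. A reader of those tables would not know that reported late related events had been left out, because the change of definition is not declared.

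**Working it through.** The plan states no figure on this point that could be reproduced. The check is a comparison of texts, a count of tables and one line of arithmetic.

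**1. Follow one event through the plan.** Take an SAE with a clear onset date more than 28 days after last dose, judged related.

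| Rule | Source | Result |
|---|---|---|
| Must it be reported? | Protocol 10.2.2.3; schedule footnote 30 | Yes, with no time limit |
| Treatment-emergent under the protocol? | Protocol 12.5.3 | Yes |
| Treatment-emergent under the SAP? | SAP 12.2 | No |
| In an AE incidence table? | SAP 12.2 list | No |
| In a patient listing? | End of SAP 12.2; protocol 12.5.3 | Yes |
| In the death listing and cause-of-death summary? | SAP 12.4 | Only if fatal |

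**2. Count the tables.** SAP 12.2 lists:
- one overview;
- three incidence tables (by class and term, the related version, and by decreasing frequency);
- two tables by worst grade (all and related);
- three by action taken (delayed or interrupted, reduced, discontinued);
- two of serious events (all and related);
- two of fatal events (all and related).

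1 + 3 + 2 + 3 + 2 + 2 = 13. All 13 are restricted to treatment-emergent events, so none would include the event in step 1.

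**3. What the window does not lose.**
- It works on onset. An event that starts by day 28 and later becomes serious or fatal is still tabulated.
- An event whose treatment-emergent status cannot be determined from its start date is counted as treatment-emergent.
- An event with missing relatedness goes into the related table.
- If alternate anticancer therapy starts before day 28, the SAP window is wider than the routine recording period, so no recorded event is dropped there.

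The gap is therefore one class: related SAEs with a known onset after day 28.

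**4. Size per patient.** Planned arm sizes are 200 (CDX-011) and 100 (capecitabine), from protocol 12.2 and SAP 5. The change in a table's rate for one affected patient not already counted in that table is 1/n:
- CDX-011: 1/200 = 0.5 percentage points.
- Capecitabine: 1/100 = 1.0 percentage point.

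These are planned randomized numbers. The safety population in SAP 6.2 counts treated patients, so the actual denominators may be slightly smaller.

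**5. Range.** The documents give no rate of late related SAEs. Purely as an assumption, 0 to 4 such patients on CDX-011 would mean an understatement of 0 to 4/200 = 0 to 2.0 points. This shows the scale and is not an estimate.

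**The case against.** The case for leaving the SAP alone has real content.

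- **The 28 days come from the protocol.** Routine recording stops there or earlier, so the protocol's open-ended definition is nearly closed in practice. This stands, and it is why the gap is narrow. But 10.2.2.3 makes an explicit exception for late related SAEs, and the SAP window does not carry that exception into the tables.
- **The SAP may change the protocol's plans.** Protocol Section 12 says so, and requires an amendment only for major changes to the primary endpoint or its analysis. The narrower window is therefore permitted. What is missing is a record of it in Section 14.
- **The events remain visible.** Listings, the death listing and the cause-of-death summary still show them. This stands, and a reader should not infer that late related events vanish from the report. However, a listing gives no incidence by arm, and the cause-of-death summary covers fatal cases only and is not described as showing relatedness. Protocol 12.5.3 mentions further SAE summaries only as something that may be provided.
- **A uniform window is cleaner.** Up to day 28 all events are in principle recorded, while later ones are selected on the investigator's causality judgment in an open-label trial, with follow-up contacts every 12 weeks and possibly by telephone. Mixing the two could distort the comparison of arms. This stands and shapes the remedy: late events should be separately identifiable.

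A reader might also infer that the alternate-therapy clause creates a second loss of data. It does not, because the SAP window is the wider one there. Nor should the window be cut at alternate therapy to match. That would make it narrower than both documents' definitions and could drop events that had been recorded.

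**Conclusion.** The point holds for one class of event. Followed as written, the SAP leaves a related SAE with a known onset after day 28 out of the related-serious and related-fatal counts by arm, although the protocol requires it to be reported and its own definition would count it. The rule can only lower those counts, and the change is undeclared.

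The size is unknown. It is about 0.5 points (CDX-011) or 1.0 point (capecitabine) per affected patient on planned arm sizes, provided that patient is not already in the table for an earlier event, and zero if no such event occurs. A reader might go further and say that a sizeable share of related deaths would be hidden. The documents give no count of related deaths or late events to support that, and all on-study deaths remain listed and summarized by cause. Nor does any passage require the incidence tables to reconcile with individual expedited reports. No efficacy analysis is affected. The change is worth making because it is cheap and concerns serious, drug-related events.

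**What to change.** 1. Keep the 28-day window for the general treatment-emergent tables, and do not shorten it at the start of alternate anticancer therapy.
2. In the treatment-related serious and treatment-related fatal tables, count SAEs assessed as related, or with relatedness missing, at any time after first dose. Alternatively, leave those tables as they are and add a parallel summary by arm of the same events. Either way, flag onsets after day 28 so that they can be read separately.
3. State in SAP Section 14 that the window in 12.2 departs from protocol 12.5.3, and how late related SAEs are handled.

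**Cost.** SAP wording and one programming flag, with no new data. Reported related-SAE rates may rise slightly. Late events are selected on investigator-judged relatedness without blinding, so differences between arms in that part need caution. If the existing tables are extended, the related-serious table may contain patients absent from the all-causality serious table, and a footnote should say so. The parallel summary avoids this.
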